#### 4.4 blood test

A blood sample (fresh heparinized blood) is taken from each patient, with which a lymphocyte activation test is carried out in vitro. For this purpose, the samples are sent overnight to the [name] / LMU Munich. There, lymphocytes and monocytes are isolated from the samples and incubated in vitro with titanium particles and on titanium plates from Astra, Camlog, Dentsply, Nobel Biocare and Straumann. After several days of culture, the release of inflammatory cytokines is measured (IL-1, IL-6, IL-8, interferon  $\gamma$ , TNF $\alpha$ , TNF $\beta$ , MMPs, etc.). Furthermore, a DNA bank for further polymorphism studies is created from a small additional sample and the CRP, beta crosslaps and HbA1c values are measured from the serum sample obtained.

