### 1. Aim of the study

The aim of the present multi-centre, cross-sectional study is to determine the prevalence and incidence of mucositis and peri-implantitis. Furthermore, with the help of a cytokine analysis of peri-implant swab samples and of blood lymphocytes or monocytes on titanium platelets and particles *in vitro*, the tolerance of titanium in relation to the clinical conditions will be examined. In total, a maximum of 200 patients will be examined at 10 centers over a period of 6 months using clinical, genetic and microbiological parameters.

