#### 4. Course of studies

##### 4.1 General medical history

As part of the survey of the general anamnesis, the underlying internal diseases of all patients are recorded. In particular, questions are asked whether the patient has diabetes mellitus, whether bisphosphonates or acetylsalicylic acid are regularly taken and whether there are allergies. In addition, the patients' smoking habits are asked about.

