### 5. Evaluation

Based on the clinical and radiological findings, the prevalence of mucositis and peri-implantitis in all patients is statistically recorded with the software program ImpDat (Kea GmbH, Pöcking). In addition, it is checked whether there is a correlation between the occurrence of peri-implant inflammation and the genetic, immunological and microbial factors also recorded.

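### Does naming serum as the specimen for HbA1c in section 4.4 call for a change to the plan?

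*Protocol*

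**What the plan says.** Section 4.4 of the protocol describes the blood work. It opens: "A blood sample (fresh heparinized blood) is taken from each patient, with which a lymphocyte activation test is carried out in vitro". It then says that "a DNA bank for further polymorphism studies is created from a small additional sample", without naming a tube type for that sample. The same sentence ends with three routine laboratory values: "the CRP, beta crosslaps and HbA1c values are measured from the serum sample obtained".

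Two other sections show what the study does with its measurements. Section 1 says patients will be examined "using clinical, genetic and microbiological parameters". Section 5 sets out the prevalence of mucositis and peri-implantitis from clinical and radiological findings, and adds that "it is checked whether there is a correlation between the occurrence of peri-implant inflammation and the genetic, immunological and microbial factors also recorded". Diabetes is covered in the medical history (section 4.1), where "questions are asked whether the patient has diabetes mellitus".

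**The concern.** HbA1c is by definition glycated haemoglobin, and haemoglobin sits inside red cells. Serum is what remains once blood has clotted and the clot and cells have been removed. A laboratory holding only serum therefore has no valid material for the assay.

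On a literal reading, the protocol promises a measurement that its named specimen cannot give. The blood comes from up to 10 centres, six of them private practices, and a centre that sent only spun serum could not recover HbA1c from that tube afterwards. HbA1c is also the only laboratory measure of glycaemia in the protocol; the other information on diabetes is what the patient reports. If the text were followed to the letter, the study could lose this variable for every patient. That would matter if HbA1c served as an outcome, a risk factor under test or an adjustment variable.

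**Working it through.** No alpha, power, effect size or sample-size figure is involved, and the protocol gives no number to reproduce. The check sets the sections side by side.

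1. **Is the sentence really about HbA1c in serum?** Yes. Three analytes share one verb and one specimen, and the grammar allows no other reading. The error concerns HbA1c only, since serum suits CRP and beta crosslaps.

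2. **Is it corrected elsewhere?** No. Both HbA1c and serum occur once in the protocol, in this one sentence. No section assigns a whole-blood aliquot to HbA1c.

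3. **Which specimens does section 4.4 describe?**

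| Specimen | Stated use | Tube type given |
|---|---|---|
| Main blood sample | Lymphocyte activation test | Heparinised |
| Small additional sample | DNA bank | None |
| Serum sample | CRP, beta crosslaps, HbA1c | Mentioned as already obtained; no draw described |

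Heparinised blood is anticoagulated, so separating it gives plasma and not serum. The serum sample thus has no antecedent in the section. The phrase reads more naturally as a loose reference to blood already taken than as a decision to run HbA1c on serum.

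4. **Which stated analyses use HbA1c?**

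| Stated aim or analysis | Uses HbA1c? |
|---|---|
| Prevalence and incidence of mucositis and peri-implantitis (section 1) | No |
| Titanium tolerance through cytokine release (section 1) | No |
| Prevalence from clinical and radiological findings (section 5) | No |
| Correlation with genetic, immunological and microbial factors (section 5) | Not named, and a glycaemic marker is not naturally any of the three |

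Count of stated analyses that depend on HbA1c: 0.

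5. **How many values could be affected?** The maximum enrolment is 10 centres × 20 patients = 200, with one HbA1c value each.
   - Lower bound: 0, assuming the laboratory uses whole blood despite the wording.
   - Upper bound: 200, assuming the text is followed literally for every patient.

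   This is the whole possible range, so it carries no information about likely loss. The upper bound also requires that nobody at any centre or laboratory notices a specimen mismatch throughout the study.

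6. **What remains if every HbA1c value were lost?** Diabetes status from the history remains, as do all the clinical, radiological, genetic, microbiological and cytokine data. Every entry in the table under step 4 can still be produced in full.

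**The case for a change.** The strongest case for a change is that the specimen for a laboratory test is protocol content. It is not something a statistical analysis plan would supply, and here the protocol does not merely omit it but states it wrongly. The sentence is complete, so it cannot be blamed on text extraction or redaction. Correcting it would cost one sentence and at most one small extra tube at a draw that takes place anyway. With ten centres drawing blood, a clear instruction is better than relying on someone to spot the mismatch.

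Much of this stands. The wording is wrong, and an editor revising section 4.4 would have good reason to tidy it. What does not follow is that the plan changes. A correction earns its place in a statistical review when it alters an estimate, a bias, a conclusion or a safety outcome, and this one alters none of them.

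The slip is also wider than HbA1c. The section describes no serum draw for any of the three analytes, so rewording HbA1c alone would leave the mismatch between heparinised blood and serum in place. That supports reading the passage as loosely phrased. Tube types for individual analytes are commonly settled in laboratory instructions, where both points would come up together. Odd phrasing elsewhere, such as calling the implants helical in section 3, suggests an imperfect translation, although that is inference and not proof.

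**Conclusion.** The observation is correct, but no change to the plan follows. Section 4.4 names the wrong specimen for HbA1c through what is most plausibly a clerical slip. The number of stated analyses affected is zero, so the prevalence estimates and the correlations in section 5 are the same whether or not the sentence is reworded.

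This rests on three assumptions:

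- **HbA1c is descriptive background.** That is how the protocol reads. The statistical analysis plan was not available for this review. If it uses HbA1c as an adjustment variable or a tested risk factor, the specimen actually used would need to be confirmed before those values are analysed.
- **The laboratory will use a specimen that can give the result.** This is likely, because serum offers it nothing to assay and anticoagulated blood is taken from each patient. The protocol does not document it.
- **Self-reported diabetes is enough for the stated purposes.** Section 5 names no glycaemic factor, so nothing in the protocol asks for more.

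Confidence is high that the specimen is misnamed. There is no basis for claiming that any data would be lost.

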#### 4.5 IL-1 polymorphism analysis

With the help of a brush (GenoType® PST® plus, Hain Lifescience GmbH, Nehren), a smear is also taken in the peri-implant area. The brushes are then placed in a test tube and examined in the laboratory for an IL-1 polymorphism (Bioscientia GmbH, Ingelheim).

#### 4.6 Microbiological test parameters

A microbiological examination is carried out on all patients. For this purpose, the qualitative and quantitative presence of *Aggregatibacter actenomycetemcomitans* (Aa), *Porphyromonas gingivalis* (Pg), *Prevotella intermedia* (Pi), *Tannerella forsythia* (Tf), *Treponema denticola* is determined with a marker germ analysis (micro-IDent® plus, Hain Lifescience GmbH, Nehren) (Td), *Peptostreptococcus micros* (Pm), *Fusobacterium nucleatum* (Fn), *Campylobacter rectus* (Cr), *Eubacterium nodatum* (En), *Eikenella corrodens* (Ec) and *Capnocytophaga* sp. (C.sp.) examined. For this purpose, after the examination area has dried, a sterile paper tip is inserted to the bottom of the respective peri-implant pocket and left there for about 20 seconds. These are then placed in a test tube and examined in a laboratory (Bioscientia GmbH, Ingelheim).

#### 4.7. Quantitative determination of the protein aMMP-8

Furthermore, a quantitative determination of the tissue-degrading protein aMMP-8 is carried out in all patients (Bioscientia GmbH, Ingelheim).

### 5. Evaluation

Based on the clinical and radiological findings, the prevalence of mucositis and peri-implantitis in all patients is statistically recorded with the software program ImpDat (Kea GmbH, Pöcking). In addition, it is checked whether there is a correlation between the occurrence of peri-implant inflammation and the genetic, immunological and microbial factors also recorded.

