### 3. Inclusion criteria for patients

- Presence of at least one helical dental implant made of cp-Ti with an insertion date after April 1st, 2001
- No other titanium implants in the body

- Regular participation in a recall

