##### Bleeding on probing (BOP):

Determination 30 seconds after probing at 6 points around the implant (mesio-facial, mid-facial, disto-facial, mesio-oral, mid-oral, disto-oral) to determine the peri-implant inflammation status.

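### Section 5 plans a correlation of peri-implant inflammation with biological factors but gives the recorded smoking, diabetes and acetylsalicylic acid data no stated role, so the immunological and microbial associations may be confounded

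*Protocol*

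**What the plan says.** Section 5 (Evaluation) is the only analysis text in the protocol. It first takes the prevalence of mucositis and peri-implantitis from the clinical and X-ray results. It then adds that "it is checked whether there is a correlation between the occurrence of peri-implant inflammation and the genetic, immunological and microbial factors also recorded". It names three classes of factor and one kind of analysis, a correlation.

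The protocol also collects background variables. In section 4.1, "questions are asked whether the patient has diabetes mellitus, whether bisphosphonates or acetylsalicylic acid are regularly taken and whether there are allergies", and "the patients' smoking habits are asked about". In section 4.4, "CRP, beta crosslaps and HbA1c values are measured from the serum sample obtained". No section says what smoking, diabetes, HbA1c or acetylsalicylic acid are for in the analysis.

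On design, section 1 describes a "multi-centre, cross-sectional study". Section 3 lists three entry conditions: the implant itself ("Presence of at least one helical dental implant made of cp-Ti with an insertion date after April 1st, 2001"), no other titanium implant in the body, and regular recall. None concerns smoking, diabetes or medication.

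On the outcome, section 4.2 records bleeding on probing "to determine the peri-implant inflammation status".

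**The concern.** In an unrandomised comparison, a variable that affects both the disease and the marker creates an association between them, or cancels one, unless design or analysis deals with it. Smoking and diabetes are plausible variables of this kind for the peri-implant flora and for inflammatory markers. Acetylsalicylic acid raises a different problem: through its effect on platelets it may make a site bleed more readily, which moves the recorded outcome without any change in inflammation. These mechanisms are general background and are not stated in the protocol.

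The associations are not incidental. Section 1 makes the tolerance of titanium in relation to clinical status part of the aim. A finding on cytokine release or on an organism could partly reflect who smokes or has diabetes, and a real association could be hidden. The variables needed to examine this are already being recorded.

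**Working it through.** **Step 1. Is there control anywhere in the document?**

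| Route | Protocol | Result |
|---|---|---|
| Randomisation | Section 1: cross-sectional | none |
| Restriction at entry | Section 3: three criteria | none on these variables |
| Measurement | Sections 4.1 and 4.4 | smoking, diabetes, HbA1c, acetylsalicylic acid recorded |
| Stated analysis | Section 5: correlation with three factor classes | no role stated for them |

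Allergies, also asked about in section 4.1, could be counted as immunological. Smoking, diabetes, HbA1c and acetylsalicylic acid do not fit any of the three classes naturally.

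**Step 2. How large could the effect be?** The protocol gives no disease rate, marker frequency, smoking frequency, effect size or power, so there is no figure of its own to reproduce. All inputs in this step are assumptions.

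Let a share p of patients smoke. Let disease risk be d1 in smokers and d0 in non-smokers, and marker frequency m1 and m0. Within each smoking group the marker has no effect (odds ratio 1.00). Collapsing over smoking:

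- marker and disease: A = p·m1·d1 + (1−p)·m0·d0
- marker, no disease: B = p·m1·(1−d1) + (1−p)·m0·(1−d0)
- no marker, disease: C = p·(1−m1)·d1 + (1−p)·(1−m0)·d0
- neither: D = the remainder
- crude odds ratio = (A/B)/(C/D)

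| p | d1, d0 | m1, m0 | A, B, C, D | Crude OR |
|---|---|---|---|---|
| 0.20 | 0.30, 0.20 | 0.50, 0.40 | 0.094, 0.326, 0.126, 0.454 | 1.04 |
| 0.25 | 0.40, 0.18 | 0.60, 0.40 | 0.114, 0.336, 0.121, 0.429 | 1.20 |
| 0.25 | 0.40, 0.18 | 0.70, 0.40 | 0.124, 0.351, 0.111, 0.414 | 1.32 |
| 0.30 | 0.50, 0.20 | 0.70, 0.35 | 0.154, 0.301, 0.136, 0.409 | 1.54 |

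**Step 3. Bias against sampling error.** With 200 patients and one observation each, the standard error of the log odds ratio is √[(1/A + 1/B + 1/C + 1/D)/200], which is about 0.31 to 0.35 in these four cases. Dividing ln(OR) by it gives a bias of about 0.11, 0.55, 0.83 and 1.38 standard errors, in table order.

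**Step 4. A wider set of assumptions.** Take confounder frequency 20–30%, disease risk without the confounder 15–30%, marker frequency without it 30–50%, confounder–disease odds ratio 2–4 and confounder–marker odds ratio 1.5–3.

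- No true association: the crude odds ratio is 1.05 to 1.41. At 200 patients and two-sided 5%, the chance of a significant result in the biased direction is about 3% to 19%, against 2.5% nominal.
- True conditional odds ratio of 2, marker frequency 50%, confounder inversely related to the marker (odds ratio 1/2 to 1/3): the crude odds ratio is 1.38 to 1.83 and power about 17–55%. If the confounder is unrelated to the marker, the figures are 1.88 to 1.98 and about 51–65%. That smaller shortfall from 2 is non-collapsibility of the odds ratio and not confounding.

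**Step 5. What adjustment can the data carry?** The Step 2 cases imply 44 to 58 diseased patients among 200 (22% to 29%). Nine fixed centre terms, three covariates and the marker make 13 parameters: 44/13 = 3.4 to 58/13 = 4.5 cases per parameter. Without the fixed centre terms there are 4: 44/4 = 11 to 58/4 = 14.5.

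**The case against.** **Scope.** Covariates and model form are often left to a statistical analysis plan. One may exist here but was not available. Section 5 is a short outline that never calls the correlation unadjusted and never rules other variables out. A reader might infer that the sponsor has decided against adjustment, or that the background data will go unused. The text does not support that: it is silent on their role. What stands is narrower. The protocol does fix which factors are analysed and how, and that statement, taken as written, leaves the associations open to confounding.

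**Mechanism.** A reader might also infer that all three factor classes are equally exposed, or that acetylsalicylic acid distorts the cytokine test. Neither is shown. Habits and medication do not alter the IL-1 genotype (section 4.5). Blood for the cytokine test travels overnight, cells are isolated, and release is measured after several days of culture (section 4.4); nothing shows that a drug effect lasts through this. Bleeding is also only one input to disease status, beside probing depth and comparison with earlier X-rays, so any shift from acetylsalicylic acid is partial. These limits are accepted.

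**Size.** Every numerical input is assumed, the four worked cases concern smoking only, and three of the four biases are below one standard error. This is correct and rules out any claim of a large known bias. It does not remove a systematic error that the recorded data could reduce.

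**Cost.** Adjusting for ten centres by fixed terms would make the model fragile (Step 5). This stands, and the remedy avoids it.

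**Conclusion.** The point holds in limited form. Section 5 states a correlation with genetic, immunological and microbial factors and assigns no role to the smoking, diabetes/HbA1c and acetylsalicylic acid data, and nothing in the design controls them. The immunological and microbial associations are therefore open to confounding by smoking and diabetes, and the bleeding component of the outcome may shift with acetylsalicylic acid.

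The size cannot be taken from the protocol. The illustrative range for a null marker, 1.04 to 1.54, rests wholly on assumed frequencies and is near 1 when the links are weak. No size is offered for acetylsalicylic acid or diabetes separately. The prevalence aim is not affected, and the genotype association is little affected. The change is worth making because it improves a stated aim with data already planned.

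**What to change.** Add to section 5 that each association of peri-implant inflammation with an immunological or microbial factor is estimated in a regression with a small adjustment set fixed in advance: smoking and diabetes (history or HbA1c), plus regular acetylsalicylic acid use where the outcome relies on bleeding. Report the unadjusted estimate beside the adjusted one. Handle centre by stratification or a random effect rather than nine fixed terms. Where two implants per patient are analysed (section 4.2), the model should also allow for their correlation.

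Repeating the analysis without acetylsalicylic acid users is optional. It would show whether a result depends on drug-related bleeding, but it reduces the sample.

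The cost is wording only: no new data and no extra visits. The price in the analysis is a few degrees of freedom and slightly wider intervals.
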